5.3.2 Female Specific Exclusion Criteria

1. Are pregnant;
2. Are at a high risk for becoming pregnant or likely to become pregnant during treatment;
3. Are breast-feeding or considering breast-feeding during the course of the study;
4. Have a known history of PCOS with another clinically significant abnormality (eg, metabolic syndrome or elevated lipids);

5. Are unable or unwilling to maintain compliance with birth control measures.

5.3.3 Concurrent Disease Exclusion Criteria

1. Have a known history or presence of any clinically significant unstable medical condition(s) which, in the opinion of the investigator, may pose a risk to the safety of the subject including any previous history of gastrointestinal disease (eg, Crohn's disease, ulcerative colitis, pancreatitis, etc) or a history of bone disease;
2. Have any skin disease or other condition that may interfere with the evaluation of recalcitrant nodular acne;
3. Have a lifetime history of major depressive, manic, hypomanic, or mixed episodes, or are receiving lithium;
4. Have reported past or current psychotic symptoms (assessed with the Psychosis Module of the Structured Clinical Interview DSM-IV clinical trials [SCID-CT]);
5. Reported of any suicidal behavior (including attempts, interrupted attempts, aborted attempts, or other preparatory behaviors) within the past year or serious suicidal ideation (defined as any suicidal ideation of Type 4 or 5 on the Columbia Suicide Severity Rating Scale [C-SSRS]) in the past year;
6. Have a known history or suspected carcinoma;
7. Have a known history of liver or kidney disorders (hepatic and renal insufficiency);
8. Have a known history or current pseudotumor cerebri (benign intracranial hypertension).

5.3.4 Hypersensitivity/Allergy Exclusion Criteria

1. Hypersensitivity or idiosyncratic reaction to isotretinoin, vitamin A and/or any other drug substances with similar activity;
2. Allergy to soybeans, soybean oil, or any other ingredients in the study.

5.3.5 Prohibited Medication Before and/or During the Study

5.3.5.1 Medication Prohibited Before or During the ATP

1. Tegison (etretinate) or Soriatane (acitretin): any previous treatment at any time;
2. Vitamin A supplements: Subjects with known daily intake of >1000 pg for males and >800 pg females will be excluded from the study. During the course of the study, subjects are to limit their intake of vitamin A supplements to <1000 pg for males and <800 pg for females;
3. Systemic corticosteroids (within 30 days prior to Baseline). Very low dose inhaled corticosteroids are allowed;
4. Topical corticosteroids applied to the face within 7 days prior to Baseline;
5. Spironolactone and its derivatives used within 30 days prior to Baseline and during both phases of the study;

6. Phenytoin;
7. Antimicrobials:
 - a. Oral antibiotics or topical antibiotics (on the face) within 14 days of Baseline and throughout the ATP.
 - i. Short courses of antibiotics may be administered during the ATP for purposes other than acne therapy at the discretion of the investigator.
 - ii. (Note: some antibiotics, eg, rifampin and penicillin derivatives, have the potential to decrease the effectiveness of birth control pills. This needs to be taken into consideration by the study investigator).
 - b. Tetracyclines: Isotretinoin use has been associated with a number of cases of pseudotumor cerebri (benign intracranial hypertension), some of which involved concomitant use of tetracyclines. Therefore, concomitant treatment with tetracyclines should be avoided.
 - i. Early signs and symptoms of pseudotumor cerebri include papilledema, headache, nausea and vomiting, and visual disturbances. An ophthalmologist should evaluate subjects for papilledema if these suggestive symptoms develop.
 - ii. Also, if these symptoms occur or if the investigator and/or ophthalmologist judge this to be appropriate, tell the subjects to discontinue isotretinoin immediately and refer them to a neurologist for further evaluation and care. Such cases should be reported to the designated Medical Monitor.
8. Any other medication used to treat acne, including over-the-counter and prescription topical therapies and systemic medications. These should not be used within 14 days of Baseline or during either phase of the study;
9. Microdose progesterone preparations for contraception in female subjects. The subject must stop using the microdose preparations and switch to an iPLEDGE acceptable form of oral contraceptive under the direction of her primary physician or gynecologist;

Note: Female subjects using combined oral contraceptives are eligible for the study and will be allowed to continue using them if they have been on the contraceptive for at least the last 3 months prior to Screening and there has been no improvement in the status of their acne.
10. Medications that may decrease the effectiveness of birth control products when used concomitantly with hormonal contraceptives. The study investigators are advised to EXERCISE CAUTION and consult the package insert of the medications prior to administering them to females of childbearing ability. Drugs that are known to decrease the effectiveness of hormonal contraceptives should not be used concomitantly with the study medication;
11. Any other medication that the investigator judges to have an adverse effect when given with isotretinoin or any medication disallowed in the protocol;

12. Any physical therapies (ie, PDT, laser, lights, peels, microdermabrasion, etc) within 1 month prior to Baseline and during both phases of the study;
13. Over-the-counter products that may worsen acne, eg, products that contain high iodine levels, such as kelp;
14. Herbal products (St. John's Wort, red clover, milk thistle, etc).

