2.3 Benefit-Risk Assessment

Isotretinoin is currently regarded as the most effective treatment option for severe nodular or nodular cystic acne, due to the ability of this compound to induce complete and prolonged remission, with an expected cure rate of 80% to 85%.⁴ The duration of suffering is shortened,

and the amount of scarring is typically reduced. The current study offers subjects with severe acne the opportunity to receive a highly effective treatment with a 2-year follow-up period, during which re-treatment with Absorica® (isotretinoin) or another anti-acne medication will be offered if a relapse occurs.

More than 12 million subjects have been treated with isotretinoin since its approval in 1982.⁴ Side effects include those of the mucocutaneous, musculoskeletal, and ophthalmic systems, as well as headaches and central nervous system effects. Most of the adverse effects are reversible after the drug is discontinued.⁸

Isotretinoin is a known teratogen, with the overall risk of birth defects estimated to be about 30%.⁵ Female subjects of childbearing potential must participate in a risk management program such as iPLEDGE™ to minimize pregnancy risk.

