3.0 TRIAL OBJECTIVES AND PURPOSE

3.1 20-Week Active Treatment Period (ATP)

The primary objective during the 20-week ATP of the study will be to investigate the quality of life (QOL) of subjects who are taking Absorica® (isotretinoin) capsules twice daily (bid) without food for the treatment of severe recalcitrant nodular acne.

The secondary objective during the 20-week treatment period will be to investigate the efficacy and safety of Absorica® (isotretinoin) taken bid without food during the ATP.

Safety will be assessed through the monitoring of AEs, laboratory test results, vital signs, and physical examinations.

3.2 104-Week Post-Treatment Period (PTP)

The primary objective during the 104-week PTP of the study is to determine both the time to retreatment and the proportion of subjects who require retreatment with oral isotretinoin during a 2-year PTP.

The secondary objectives during the PTP are:

- To investigate the QOL at the end of the 2-year PTP;
- To investigate the severity of the acne over time, as measured by the Investigator's Global Assessment (IGA) and lesion counts;
- To document any acne treatment (prescription and/or over-the-counter [OTC]) used by those subjects;
- To evaluate the long-term safety during the 2-year PTP.

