Subjects who are prescribed a second course of treatment Absorica® or any other formulation of isotretinoin during the PTP will be withdrawn from the study after their lesion count and IGA are recorded. Subjects who use OTC or oral non-isotretinoin acne treatment can remain in the study, but their medication use is to be recorded.

The study design is summarized in [Figure 4-1](#).

Figure 4-1 Study Design

Note: EOT = end of treatment; EOS = end of study

a. A mandatory, confirmatory pregnancy test for female subjects of childbearing potential must be conducted according to the iPLEDGE guidelines.

b. Week 2 safety laboratory tests.

c. 4 Week post treatment safety follow-up

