4.2.2.2 Secondary Endpoints for the PTP

Secondary endpoints for the PTP will be:

- The proportion of subjects who require treatment with a prescription anti-acne medication other than oral isotretinoin at any time during the PTP;
- The proportion of subjects who use an over-the-counter (OTC) anti-acne medication at any time during the PTP;
- The severity of acne (lesion count and IGA) at the time of retreatment in subjects treated with a prescription or OTC anti-acne treatment;
- The severity of acne (lesion count and IGA) at each visit;
- The time to retreatment with a prescription or over-the-counter (OTC) anti-acne medication at any time during the PTP;
- The acne-QOL at the end of the PTP;
- Safety as assessed through the monitoring of AEs, laboratory test results, vital signs, and physical examinations.

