6.5 Prior and Concomitant Therapy

All medications, including OTC drugs, taken within 30 days prior to the start of the study will be recorded at Screening. Thereafter, a record of all medications and supportive therapy taken during the course of the study will be made. Information regarding the total daily dose, route of administration, start and discontinuation dates, and indication are to be recorded on the subject's eCRF.

Restricted or prohibited medications and treatments are listed in the Exclusion Criteria ([Section 5.3.5](#)).

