6.8 Disallowed Medications

Subjects who had used the following medications at any time are to be excluded from the study:

- Tegison® (etretinate).

- Soriatane® (acitretin).

Use of the following medications, preparations, and treatments is disallowed as noted below.

- 30 days prior to Baseline and throughout the study (both ATP and PTP):
 - Systemic corticosteroids.
 - Spironolactone and its derivatives.
- 14 days prior to Baseline and throughout the study:
 - Antibiotics. Tetracyclines are prohibited during the study. Short courses of other antibiotics can be administered during the study at the discretion of the investigator. [Note: Per [Section 5.3.5](#), antibiotics and tetracyclines are prohibited during ATP but allowed during the PTP]
 - Phenytoin (eg, Dilantin);
 - Any other medication used to treat acne (both ATP and PTP).
- 7 days prior to Baseline:
 - Topical corticosteroids.
- During the study (both ATP and PTP):
 - Vitamin A supplements > 1000 µg for males and >800 µg for females (ATP and PTP)
 - Herbal products (St. John's Wort, red clover, milk thistle, etc).
 - Microdose progesterone preparations (see [Section 6.6](#)).
 - Oral contraceptives with approved anti-acne indication for nodular acne (eg, Ortho Tri-Cyclen®, Yaz®, and Estrostep®). Females using oral contraceptives with anti-acne activity are allowed to continue using them if they had been on the contraceptive for at least the last 3 months prior to screening and there was no improvement in the status of their acne. For subjects who remain on an oral contraceptive during the PTP, it is preferred that they continue on the same medication as in the ATP; if any change is required, it is preferred that the medications named above be avoided. All medications taken should be documented.

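### The ban on other, non-antibiotic acne medication extends into the PTP, where the protocol elsewhere offers such treatment and four of seven secondary endpoints measure it

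*Combined protocol and SAP*

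**What the plan says.** Two sections impose the ban. Section 5.3.5.1 item 8 concerns any other acne medication, "including over-the-counter and prescription topical therapies and systemic medications", and sets its period: "These should not be used within 14 days of Baseline or during either phase of the study". Section 6.8 has a matching bullet, "Any other medication used to treat acne (both ATP and PTP"), under a lead-in that already runs from 14 days before Baseline through the whole study.

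Other sections expect the same treatment to be used in the PTP:

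- Section 2.3 says that on relapse Absorica "or another anti-acne medication will be offered if a relapse occurs".
- Section 3.2 makes it a PTP secondary objective: "To document any acne treatment (prescription and/or over-the-counter [OTC]) used by those subjects".
- Section 4.1: "Subjects who use OTC or oral non-isotretinoin acne treatment can remain in the study, but their medication use is to be recorded".
- Section 4.2.2.2 lists as its first endpoint: "The proportion of subjects who require treatment with a prescription anti-acne medication other than oral isotretinoin at any time during the PTP". Three further endpoints also depend on prescription or OTC acne treatment.
- Section 7.2.7 brings a subject with a flare to an unscheduled visit, where treatment options are considered.

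Antibiotics are handled separately. Item 7a of Section 5.3.5.1 restricts oral and facial topical antibiotics up to the end of the ATP, and a bracketed note in Section 6.8 says antibiotics and tetracyclines are allowed in the PTP. The sentence before that note still prohibits tetracyclines for the whole study.

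**The concern.** A study cannot measure how often subjects need other acne treatment over two years while forbidding that treatment over the same two years. If the ban is followed, it suppresses the events that the endpoints count and withholds the relapse care described in Section 2.3. If it is ignored, ordinary use becomes a protocol deviation.

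The practical risk is uneven conduct. A site relying on Section 5.3.5 or 6.8 could decline to treat a flare, or could withdraw a user under the discretionary non-adherence clause in Section 5.4. The only discontinuation for retreatment that the protocol actually states is for a further course of isotretinoin (Sections 4.1 and 7.2.8). A site relying on Section 4.1 would treat, record and continue. Section 8.1 combines data from all centers, so the pooled proportions and times could partly reflect which section each site followed.

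**Working it through.** The protocol gives no figure to reproduce. The check is a count and a comparison of texts.

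**1. Endpoints affected.** Section 4.2.2.2 has seven bullets.

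| PTP secondary endpoint | Depends on non-isotretinoin acne treatment? |
|---|---|
| Proportion needing other prescription treatment | Yes |
| Proportion using OTC treatment | Yes |
| Severity at time of retreatment | Yes |
| Severity at each visit | No |
| Time to prescription or OTC retreatment | Yes |
| Acne-QOL at end of PTP | No |
| Safety | No |

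The count is 2 proportions + 1 severity summary + 1 time to event = 4 of 7. The synopsis carries the same seven.

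**2. Products affected.** Item 8 names three classes: OTC, prescription topical and systemic. Section 4.1 expressly covers OTC and oral use, so 3 − 2 = 1 class, prescription topicals, has no express permission there. Facial topical antibiotics come out of that remainder through item 7a. What is left is non-antibiotic prescription topicals. Sections 2.3, 3.2 and 4.2.2.2 imply that these are allowed, since none of them excludes topicals, but no section says so.

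**3. Does any text settle the conflict?**

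- *The heading of Section 5.3.5.1* refers to the time before or during the ATP. Item 8 itself reaches both phases, as do items 5 (spironolactone) and 12 (physical therapies) under the same heading, and Section 6.8 names the PTP outright. The heading therefore does not limit the ban.
- *Section 5.3.5.2*, the PTP list, does not name acne medication. It does not name spironolactone or physical therapies either, although both are expressly barred in both phases. Its silence is not permission.
- *Section 6.5* says "Restricted or prohibited medications and treatments are listed in the Exclusion Criteria" and points to Section 5.3.5 as a whole. That contains both the ban and the silent PTP list, so it does not decide the matter.
- *The note in Section 6.8* reconciles antibiotics and tetracyclines only. The acne-medication bullet in the same list keeps its reference to the PTP.

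**4. Direction of any effect.** A subject deterred from treatment does not count as a user, which lowers the relevant proportion and delays or removes a retreatment event. A subject withdrawn after OTC use has already counted for OTC, but a later prescription would not be seen; the reverse order loses a later OTC use. Both mechanisms change who enters the severity-at-retreatment summary. How many subjects would be affected is not stated and cannot be inferred.

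**The case against.** The strongest reply is that the intended design is clear. Sections 2.3, 3.2, 4.1, 4.2.2.2 and 7.2.7 all point the same way, and Section 6.7 allows medications prescribed by primary care providers during the trial, subject to the investigator's evaluation. A site looking up PTP rules would naturally turn to Section 5.3.5.2 and find no such ban. The text can even be read as a default of no other treatment, with use tolerated and recorded when it is needed. Harm requires a site to pass over all of this and then invoke a general, discretionary clause.

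Much of that stands as a limit on the consequence. It does not remove the contradiction: two sections name the PTP in the ban, nothing ranks the sections, and the tolerated-exception reading does not fit Section 2.3, where the study itself offers the treatment.

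A reader might infer more than the documents support:

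- *That all acne medication is barred in the PTP.* Item 7a and the Section 6.8 note exempt antibiotics.
- *That the four endpoints cannot be tabulated.* Sections 4.1 and 6.5 require use to be recorded, and Sections 7.2.6 and 7.2.7 review acne-related medication at Visit 9 and at Visits 10 to 14.
- *That users would drop out of the per-protocol population.* Section 8.3 applies its disallowed-medication criterion only to the 20 weeks of treatment.

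**Conclusion.** The contradiction is real and in current text, for non-antibiotic acne products in the PTP. It touches four of the seven PTP secondary endpoints. If sites applied the ban, the two proportions could be too low, and the time-to-retreatment and severity-at-retreatment summaries could be distorted. That rests on the assumption that at least some sites would follow Section 5.3.5.1 item 8 or Section 6.8 rather than Section 4.1.

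The size cannot be derived: the documents give no expected rate of such treatment, no PTP denominator and no indication of how many sites would apply the ban. Scaling by the planned 200 enrolled subjects or 140 ATP completers would give only the weight of one subject, not an estimate of bias.

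It would be tempting to carry the argument over to the primary PTP endpoints on isotretinoin retreatment. The documents do not support that. A deterred subject might reach isotretinoin sooner, while a withdrawn subject's later isotretinoin might go unseen, so any effect is indirect and of unknown direction. This is a modest wording correction affecting secondary endpoints, and it is worth making because it is cheap.

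**What to change.** One amendment in four places:

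1. **Section 5.3.5.1 item 8:** change the time clause so that it covers the 14 days before Baseline and the ATP only.
2. **Section 6.8:** move the acne-medication bullet out of the whole-study list to a new lead-in covering 14 days before Baseline and the ATP, and delete its parenthesis naming both periods. Editing the parenthesis alone would leave the present lead-in contradicting it. In the same section, limit the tetracycline sentence to the ATP so that it agrees with its note.
3. **Section 4.1** and 4. **Section 5.3.5.2:** state that non-isotretinoin acne treatment (OTC, oral and prescription topical) is permitted and recorded in the PTP, and is neither a deviation nor a reason for withdrawal. Except what is separately restricted in the PTP: the items in Section 5.3.5.2, spironolactone, physical therapies, and the remaining PTP restrictions in Section 6.8, including its oral contraceptive provisions.

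The cost is a wording amendment with sponsor and investigator approval (Section 9.1), and IRB approval unless it is classed as administrative (Section 12.2). It adds no visits, data or subjects.

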5.3.5.2 Medication Prohibited During the PTP

1. Tegison (etretinate) or Soriatane (acitretin);
2. Vitamin A supplements: Subjects with known daily intake of >1000 pg for males and >800 pg females will be excluded from the study during both phases of the study (29 months). During the course of the study, subjects are to limit their intake of vitamin A supplements to <1000 pg for males and <800 pg for females;
3. Systemic corticosteroids or topical corticosteroids applied to face. Very low dose inhaled corticosteroids are allowed;
4. Over-the-counter products that may worsen acne, eg, products that contain high iodine levels, such as kelp.
5. Note: During the PTP, any antibiotic therapy given for intercurrent illness (ie, upper respiratory infection, urinary tract infection) must be documented with the name of the antibiotic, dose, and duration of treatment.
6. Note: the contraception methods used by female subjects of childbearing potential during the PTP should be documented.

5.4 Discontinuation of Treatment

In accordance with legal requirements and International Conference on Harmonization (ICH) – Good Clinical Practice (GCP) guidelines, every subject has the right to refuse further participation in this study at any time and without providing reasons. A subject's participation is to be terminated immediately upon his/her request. The Investigator should seek to obtain the reason and record this on the electronic case report form (eCRF), whenever possible.

If, at the time of refusal, a study product has already been administered, the subject should be advised on follow-up safety investigations.

In the case of significant disease or intolerance of study medication, the decision to stop treatment for a given subject can be made by the investigator alone. If such a treatment discontinuation occurs, the investigator will notify the sponsor and provide medical justification.

A subject may be withdrawn from the study at any time at the discretion of the investigator for medical reasons and/or due to non-adherence to the treatment scheme and other duties stipulated in the study protocol. The reasons for early termination are to be fully documented on the eCRF.

In addition, the sponsor reserves the right to end or suspend the study at any time (see [Section 9.2](#)).

If a subject withdraws from the study, all efforts will be made to complete the final evaluation procedures at the time of termination if possible. Protocol-specified withdrawal procedures are the same as those to be performed at the End of Treatment (EOT) visit (if withdrawal occurs during the ATP) or at the End of Study (EOS) visit (if withdrawal occurs during the PTP).

Subjects discontinued for an AE will be monitored until the AE is resolved, a reasonable explanation is provided for the event, or the subject is referred to his/her own primary medical doctor. The specific AE in question will be recorded on the appropriate CRF.

Subjects who prematurely discontinue the study will not be replaced.

